7.3.4 Sponsor Responsibility for Reporting Adverse Events including Deviations and Exceptions

All Adverse Events will be reported to regulatory authorities, IRB/IECs and investigators in accordance with all applicable global laws and regulations.

Version 12, October 21, 2018. UPCC 46415: Phase I/II study of pembrolizumab in patients failing to respond to or relapsing after anti-CD19 chimeric antigen receptor modified T cell therapy for relapsed or refractory CD19+ lymphomas

This document is confidential and the property of the University of Pennsylvania. No part of it may be transmitted, reproduced, published, or used by other persons without prior written authorization from the regulatory sponsor.

Reportable Events:

Any accidental or unintentional deviation from the approved protocol, identified retrospectively, that in the opinion of the investigator or as defined by the protocol, placed one or more participants at increased risk, compromises the rights or welfare of subjects, and/or disrupts the study design, is considered a reportable event and must be reported to the Study Principal Investigator, Study Medical Monitor, IRB, and ACC DSMC within 10 working days of notification. Principal Investigator and Medical Monitor approval/acknowledgement must be received first and included in with the IRB/DSMC submission. Deviations to protect subjects from immediate harm/danger should be reported immediately following the event to the entities outlined above.

Exceptions (Prospective action):

An exception is defined as a one-time, intentional action or process that departs from the IRB and CTSRMC approved study protocol, intended for one occurrence. If this action disrupts the study progress, such that the study design or outcome (endpoints) may be compromised, or the action compromises the safety and welfare of study subjects (i.e., requests to enroll and/or treat subjects outside of the current protocol criteria), **advance documentation of Medical Monitor, IRB, and DSMC approval is required**. Principal Investigator and Medical Monitor approval must be received first and included in with the IRB/DSMC submission. All entities should be given sufficient time to evaluate this request.

Deviations (Retrospective action):

A one time, **un**intentional action or process that departs from the IRB and CTSRMC approved study protocol, involving one incident and identified retrospectively, after the event occurred. If the impact on the protocol disrupts the study design, may affect the outcome (endpoints) or compromises the safety and welfare of the subjects, the deviation must be reported to the DSMC within 5 business days and the IRB within 10 business days.

For reportable deviations, documentation of the Medical Monitor response must be submitted to the DSMC **with** the report.

Deviations that do not meet the definition above of “reportable” will be explained in a memo to file or recorded on a deviation log and will contain documentation of the **PI’s assessment** of the impact of the deviation on safety and study outcomes.

This document is confidential and the property of the University of Pennsylvania. No part of it may be transmitted, reproduced, published, or used by other persons without prior written authorization from the regulatory sponsor.

8.0 STATISTICAL ANALYSIS PLAN

8.1 Statistical Analysis Plan

8.1.1 Primary Objectives & Hypotheses

(1) Objective: To determine the safety of pembrolizumab in patients failing to respond to or relapsing after anti-CD19 chimeric antigen receptor modified T cell therapy for relapsed or refractory CD19+ lymphomas. Safety will be assessed by adverse event monitoring. Patients who have received at least one dose of pembrolizumab will be considered evaluable for safety. In this trial, success will be defined as receiving at least one dose of pembrolizumab and the lack at least possibly related adverse events leading to permanent discontinuation of pembrolizumab. Patients who experience Grade 3 or higher non-hematologic toxicity leading to permanent pembrolizumab discontinuation or any Grade 4 non-hematologic toxicity or cytokine release syndrome at least possibly related to pembrolizumab will be considered toxicity failures.

Methodology: We will use a Bayesian monitoring rule to assure that the failure rate is no greater than 30%. Monitoring will begin with the first patient. Because little information is available on the safety of this drug in lymphoma, we will assume a non-informative Beta(1, 1) prior distribution for the failure rate. We will denote the rate of pembrolizumab discontinuation as failure rate, FR, and will use the following monitoring rule in the interest of patient safety: we will stop the trial if at any time: $\Pr[\text{FR} > 0.30 \mid \text{data from the trial}] \geq 97.5\%$

That is, if at any time during the study, we can conclude that there is at least a 97.5% chance that the failure rate is greater than 30%, we will stop the study. The stopping boundaries corresponding to this probability criterion are to terminate the trial if:

$(\# \text{ of patients that experience failure}) / (\# \text{ of patients evaluated}) \geq 3/3, 3/4, 4/5, 4/6, 5/7, 5/8, 6/9, 6/10, 7/11, 7/12$. Any patient who has received at least one dose of pembrolizumab will be included in this denominator for evaluable patients if they have received at least 4 doses of pembrolizumab and not experienced toxicity OR if they have experienced any toxicity with any dose of pembrolizumab.

If the study is not terminated early, it will continue until all patients have been treated with pembrolizumab and completed all follow up evaluations.

Hypothesis: Pembrolizumab will be safely tolerated with $\leq 30\%$ of patients experiencing toxicities resulting in discontinuation of pembrolizumab

This document is confidential and the property of the University of Pennsylvania. No part of it may be transmitted, reproduced, published, or used by other persons without prior written authorization from the regulatory sponsor.

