1.0 TRIAL SUMMARY

Title	Phase I/II study of pembrolizumab in patients failing to respond to or relapsing after anti-CD19 chimeric antigen receptor modified T cell therapy for relapsed or refractory CD19+ lymphomas
Abbreviated Title	Pembrolizumab after CTL019/CTL119 for relapsed/refractory CD19+ lymphomas
Trial Phase	Phase I / II
Clinical Indication	Relapsed / refractory CD19+ B cell lymphomas after CTL019/CTL119
Trial Type	Investigator-initiated
Type of control	None. Enrollment will be offered to subjects with an unmet medical need, which is no available effective, standard therapy for relapsed / refractory CD19+ lymphomas
Route of administration	Intravenous
Trial drug, dose, route, regimen	Pembrolizumab (Keytruda [®]) 200mg fixed dose IV every 3 weeks
Trial Blinding	None
Treatment Groups	Single group
Number of trial subjects	12 evaluable subjects
Estimated enrollment period	12 months (approximately January 2016-January 2017)
Estimated duration of trial	36 months (approximately January 2016-January 2019)
Duration of Participation	24 months (12 months treatment + 12 months follow-up)
Objectives	
Primary Endpoints:
 
 1. Determine safety of pembrolizumab after CTL019/CTL119. This endpoint will be met if $\leq 30\%$ of patients develop toxicity resulting discontinuation of pembrolizumab. 2. Determine efficacy of pembrolizumab after CTL019/CTL119. This endpoint will be met if the ORR at 3 months is $\geq 35\%$.
Statistical methodology	
Primary Endpoints:
 
 1. Safety endpoint will be assessed using a Bayesian monitoring rule to ensure probability of a patient developing toxicity resulting in discontinuation of pembrolizumab $\leq 30\%$ 
Secondary Endpoints:
 
 1. ORR will be assessed using a one-sided binomial test 2. PFS, EFS, RD, and OS will be assessed using Kaplan Maier survival analysis. PFS after pembrolizumab will be compared to PFS after CTL019/CTL119 using a log rank test.

This document is confidential and the property of the University of Pennsylvania. No part of it may be transmitted, reproduced, published, or used by other persons without prior written authorization from the regulatory sponsor.

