2.0 TRIAL DESIGN

2.1 Trial Design

This is a single center, open label trial of pembrolizumab in patients failing to respond to or relapsing after anti-CD19 chimeric antigen receptor modified T cell therapy (CTL019/CTL119) for relapsed or refractory CD19+ lymphomas.

Eligible patients will have CD19+ diffuse large B-cell, follicular, or mantle cell lymphomas with no available curative treatment options, a limited prognosis of several months to <2 years anticipated survival with currently available therapies, and progressive or relapsed disease after a single intravenous dose of $5 \times 10^8 \pm 20\%$ CTL019/CTL119 administered on our currently enrolling clinical trial (NCT02030834). We anticipate enrollment of 12 total patients onto the present trial for patients not responding to, or relapsing after, CTL019/CTL119.

[figure not shown]
The safety and efficacy of pembrolizumab in this group of patients will be determined using a fixed dose of 200mg IV. This dose was previously well-tolerated and effective for treatment of patients with metastatic melanoma and NSCLC. The primary safety endpoint will be determined by assessing the rate of pembrolizumab discontinuation as well as the rate of occurrence of treatment-related adverse events (AEs), defined as NCI CTCAE version 5 grade ≥ 3 AEs are possibly, probably, or definitely related to study treatment or grade 4 cytokine release syndrome. Secondary efficacy endpoints will be assessed, including overall response rate (ORR) and progression-free survival (PFS).

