3.0 TRIAL OBJECTIVES & HYPOTHESES

3.1 Primary Objectives & Hypotheses

(1) Objective: To determine the safety of pembrolizumab in patients failing to respond to or relapsing after CTL019/CTL119 for relapsed or refractory CD19+ lymphomas.

Hypothesis: Pembrolizumab will be safely tolerated with $\leq 30\%$ of patients experiencing toxicities resulting in discontinuation of pembrolizumab

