4.2.3 Rationale for Endpoints

4.2.3.1 Rationale for Efficacy Endpoints

- 1) **Primary Objective:** To determine the safety of pembrolizumab in patients failing to respond to or relapsing after anti-CD19 chimeric antigen receptor modified T cell therapy for relapsed or refractory CD19+ lymphomas.

Although pembrolizumab has been approved for use in melanoma, there have been no studies in non-Hodgkin lymphoma and the transition to a fixed dose has not been well-studied. In previous studies of pembrolizumab, the rates of drug discontinuation due to an adverse event were 4.2% in melanoma and 2.6% in non-small cell lung cancer and the rates of drug discontinuation for any reason were 9.4% in melanoma and 21.1% in non-small cell lung cancer (see Investigator's Brochure). Additionally, given that we hypothesize that pembrolizumab may re-activate quiescent chimeric antigen receptor T cells, there is the potential for additional toxicity in patients who have previously received chimeric antigen receptor T cells. Thus, we will define safety as ≤ 30% of patients experiencing toxicities resulting in discontinuation of pembrolizumab.

This document is confidential and the property of the University of Pennsylvania. No part of it may be transmitted, reproduced, published, or used by other persons without prior written authorization from the regulatory sponsor.

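### Section 8.1.1 defines safety success and toxicity failure so that they are not complements, and no section fixes the denominator of the final 30% decision

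*Combined protocol and SAP*

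**What the plan says.** **The endpoint.** The Trial Summary (Section 1.0) calls the safety endpoint met if no more than 30% "of patients develop toxicity resulting discontinuation of pembrolizumab". Section 3.1 has the same limit for the share "of patients experiencing toxicities resulting in discontinuation of pembrolizumab", and Section 4.2.3.1 and the hypothesis in Section 8.1.1 repeat it. None of these sets a grade limit, and all require discontinuation.

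**Section 8.1.1.** Three statements bear on the event:
- Success is at least one dose and "the lack at least possibly related adverse events leading to permanent discontinuation of pembrolizumab".
- Toxicity failures, where the drug is judged a possible or stronger cause, are patients with "Grade 3 or higher non-hematologic toxicity leading to permanent pembrolizumab discontinuation or any Grade 4 non-hematologic toxicity or cytokine release syndrome".
- The monitored parameter is labelled: "We will denote the rate of pembrolizumab discontinuation as failure rate, FR".

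**Section 2.1.** "The primary safety endpoint will be determined by assessing the rate of pembrolizumab discontinuation as well as the rate of occurrence" of related Grade 3 or higher events, with CRS named at grade 4: "possibly, probably, or definitely related to study treatment or grade 4 cytokine release syndrome". No threshold is attached to the event rate.

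**Denominator.** Section 8.1.1 first makes every patient with one dose evaluable for safety. For the stopping boundaries it then counts only patients who had four doses without toxicity, or toxicity at any dose. Section 5.8 leaves toxicity-free patients removed before 3 months out of the toxicity analysis.

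**The concern.** A binary endpoint needs each patient to fall in exactly one class. Here some patients fall in both and others in neither, and only the success sentence agrees with the 30% criterion stated elsewhere. The failure sentence departs from that criterion in both directions. It leaves out lower-grade toxicities that end treatment, which lowers the rate, and it adds Grade 4 events that need not end treatment, which raises it. The net effect cannot be known in advance.

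This is the primary endpoint and the input to the stopping rule, in a trial of 12 evaluable patients. Two analysts who each follow a sentence of the plan could report opposite verdicts from the same patients. The unfixed denominator opens a second route to the same outcome.

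**Working it through.** **1. The plan's own figures.** With a Beta(1,1) prior, the posterior probability that the failure rate exceeds 0.30 after k failures in n patients is 1 − BetaCDF(0.30; 1+k, 1+n−k). Seven of the ten printed boundaries reproduce at 97.5% (for example 3/3 = 0.9919 and 7/12 = 0.9818). Three do not: 3/4 = 0.9692, 4/6 = 0.9712 and 5/8 = 0.9747. That is a separate defect and nothing below depends on it.

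The final criterion at n = 12 is 0.30 × 12 = 3.6. So 3/12 = 25.0% meets it and 4/12 = 33.3% does not.

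**2. Patients who do not fall in exactly one class**, under the protocol's own rules, all events taken as related:

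| Event | Protocol action | Success? | Toxicity failure? |
|---|---|---|---|
| Grade 4 hypothyroidism | Continue (Table 3, Section 5.2.1.2) | Yes | Yes |
| Recurrent Grade 2 pneumonitis | Permanent discontinuation (Table 3) | No | No |
| Grade 2 infusion reaction despite premedication | Permanent discontinuation (Table 4, Section 5.4.1) | No | No |

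**3. Effect on the verdict at n = 12** (illustrative counts):
- Four treatment-ending toxicities, one of them Grade 2: the criterion as worded gives 4/12 = 33.3%, not met; the failure sentence gives 3/12 = 25.0%, met.
- Three treatment-ending Grade 3 or higher toxicities plus one continued Grade 4 hypothyroidism: 3/12 = 25.0%, met, against 4/12 = 33.3%, not met.

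**4. How often this would happen.** Let q be the true rate of treatment-ending toxicity, g the share of it at Grade 2, and c the rate of Grade 4 events with drug continued. The documents give 4.2% (melanoma) and 2.6% (non-small cell lung cancer) for discontinuation due to an adverse event (Section 4.2.3.1). They give neither g nor c, so both are assumed.

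With c = 0 the failure count never exceeds the endpoint count, so

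P(opposite verdicts) = P[Bin(12, q) ≥ 4] − P[Bin(12, q(1−g)) ≥ 4].

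- q = 4.2%, g = 1/3: 0.00117 − 0.00025 = 0.0009, about 0.1%.
- q = 20%, g = 1/3: 0.2054 − 0.0646 = 0.1409, about 14%.
- q = 20%, with g = 5%, 10%, 20% and 50%: 2.6%, 5.0%, 9.4% and 18.0%.
- q = 10% and 30%, g = 1/3: 1.9% and 30.2%.

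With c = 5% and g = 1/3, the exact multinomial over both directions gives 1.1% at q = 4.2%, nearly all against the drug. At q = 20% it gives 17.4%: 10.8 points in favour of the drug and 6.6 against.

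**5. Denominator.** Suppose 14 patients are dosed, 2 leave early without toxicity and are replaced, and 4 fail. All dosed patients give 4/14 = 28.6%, met. The evaluable set gives 4/12 = 33.3%, not met. Since only toxicity-free patients are dropped, the evaluable set can only read higher.

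**The case against.** The strongest objection is size. At the only discontinuation rates the documents cite, the two definitions almost never disagree, and the examples above sit on the edge between 3 and 4 events. That stands: they show the conflict is possible, not likely. But Section 4.2.3.1 expects possible added toxicity after CAR T cells and sets the limit at 30%, so the definition has to work at rates well above 4.2%.

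The failure sentence may also be a deliberate composite, meant to make stopping sensitive to severe events whether or not treatment ends. That is a legitimate aim for a stopping rule. It does not make the composite the endpoint the other sections state.

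Several stronger readings are tempting, and the documents do not support them:
- *The failure rate means discontinuation for any cause.* The label alone could be read so. But the methodology entry in Section 1.0 says the Bayesian rule monitors toxicity resulting in discontinuation, so the label is reasonably read as shorthand.
- *Section 2.1 sets a competing primary criterion.* Its Grade 3 or higher event rate has no threshold and cannot change the 30% verdict.
- *Sections 5.8 and 8.1.1 flatly contradict each other on the denominator.* Section 5.8 and the boundary rule nearly agree. Dose 4 falls due at week 9, so they differ only for a toxicity-free patient who leaves between then and 3 months. The real tension is with the one-dose evaluability sentence. The target of 12 evaluable subjects and the replacement rule lean towards the evaluable set, but no section says it governs the final decision.
- *Grade 2 CRS treated with tocilizumab is a clear missed failure.* Section 5.4.2 ties tocilizumab mainly to hemodynamic instability and similar severity, which the CRS table mostly grades 3 or 4. The example is strained and is not relied on here.

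**Conclusion.** The defect is real and lies in the text. Success and toxicity failure in Section 8.1.1 are not complements, only the success sentence matches the 30% criterion, and the denominator of the final decision is not fixed. At n = 12, one patient can reverse the primary safety verdict through the event definition, and two replaced early leavers can do so through the denominator.

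A reader might infer that a reversal is probable. It is not at the documented rates: about 0.1% at 4.2%, or about 1% with an assumed 5% of continued Grade 4 events. It becomes material only if toxicity after CAR T cells is much higher: about 14% at a true 20% with an assumed one-third Grade 2 share, and 2.6% to 18.0% for shares of 5% to 50%. The case for correction rests on the inconsistency in a primary endpoint, not on these assumed probabilities.

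**What to change.** 1. **Endpoint.** For the final 30% decision, define failure as the complement of the success sentence: an at least possibly related adverse event of any grade that leads to permanent discontinuation. Word the failure rate as discontinuation due to such toxicity.
2. **Stopping rule.** Reconcile the toxicity-failures sentence with this. State whether each of the following counts toward stopping, and report each separately from the 30% proportion: related Grade 4 non-hematologic events without discontinuation; CRS, and at which grade; and hematologic events. Table 3, footnote 3 says hematologic changes are not treatment-limiting, but the success sentence does not exclude them. Taking Grade 4 events out of the stopping count would make stopping less likely, so that choice must be explicit and is the sponsor's to make.
3. **Denominator.** Base the final proportion on all patients with at least one dose, as the evaluability sentence in Section 8.1.1 says, with the 4-dose evaluable set as a sensitivity analysis. Limit the Section 5.8 exclusion to the interim denominator and use one cut-off there and in Section 8.1.1.

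**Cost.** These are text changes, mainly in Sections 8.1.1 and 5.8. No new data are needed, since grade, causality and action taken are already recorded (Section 7.3.2). Patients with short exposure slightly dilute the final rate; the sensitivity analysis shows by how much. The text is Version 12 of October 2018 and estimated enrollment ended in January 2017, so patients may already be classified. If so, give the amendment date and show the counts under both the current and the amended definitions. Correct the three boundaries that fall short of 97.5% as a separate item.

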³“All other immune-related AEs” excludes hematologic AEs given that hematologic changes are not considered reportable AEs or treatment-limiting toxicity (Section 7.3, Section 8.1). For grade 3-4 hematologic toxicity at least possibly related to therapy, therapy will be held until toxicity resolves to grade 0-1 or subject’s baseline.

NOTE:

For participants with Grade 3 or 4 immune-related endocrinopathy where withhold of pembrolizumab is required, pembrolizumab may be resumed when AE resolves to \leq Grade 2 and is controlled with hormonal replacement therapy or achieved metabolic control (in case of T1DM).

This document is confidential and the property of the University of Pennsylvania. No part of it may be transmitted, reproduced, published, or used by other persons without prior written authorization from the regulatory sponsor.

Dose modification for cytokine release syndrome:

If patients develop cytokine release syndrome grades 1-3 after pembrolizumab, then pembrolizumab will be held until cytokine release syndrome resolves. Once cytokine release syndrome has fully resolved, the clinical investigator has the option of restarting pembrolizumab at ½ dose (100mg) every 3 weeks. If patients develop grade 4 cytokine release syndrome or require administration of tocilizumab, pembrolizumab will be stopped due to drug toxicity.

Dosing interruptions are permitted in the case of medical / surgical events or logistical reasons not related to study therapy (e.g., elective surgery, unrelated medical events, patient vacation, and/or holidays). Subjects should be placed back on study therapy within 3 weeks of the scheduled interruption, unless otherwise discussed with the Principal Investigator and the Data and Safety Monitoring Board. The reason for interruption should be documented in the patient's study record.

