At this time it is still unknown whether CRS/MAS is beneficial or harmful to the antitumor response. Research monitoring data showed that IL6 levels were extraordinarily high during the CRS, prompting us to use an anti-IL6 receptor antibody tocilizumab to treat the CRS/MAS. The majority of patients treated with tocilizumab for CRS and MAS had rapid (within hours) resolution of dramatic fevers, and continuous improvement in hypotension and hypoxia over hours to several days, and showed improvement in biochemical evidence of CRS and MAS within 48 hours. Adult patients were treated with tocilizumab 4mg/kg or 8mg/kg. It is unclear if early treatment will negate the antitumor response. Treatment and timing of treatment of this toxicity will be at the discretion of the patient's physician and the study principal investigator, and occur in the setting of hemodynamic instability.

Management of cytokine release syndrome

Some patients who have responded to CART-19 cells have experienced a CRS. Cytokine production is required for the activation, expansion and cytolytic function of T cells and for CART-19 T cells. Therefore some degree of CRS may be a desired clinical outcome. Premature or early intervention with anti-cytokine therapy may therefore abrogate the anti-tumor efficacy of CART-19. Subsequent to this experience, selective tocilizumab (an anti-IL6-receptor antibody) therapy has been utilized (described below) with effective toxicity management and successful ongoing CART-19 T cell expansion in patients. Please note, steroids or other immunosuppressant drugs should **NOT** be used as pre-medication for pembrolizumab but may be considered in the management of CRS.

The moderate to severe cases of CRS observed required intervention with tocilizumab, with or without high dose corticosteroids, between 2 and 9 days after T cell infusion. This resulted in rapid reversal of the high persistent fevers associated with CRS in most but not all patients.

Given the dramatic clinical improvement of most patients treated with anti-cytokine therapy, patients with moderate to severe cytokine toxicities should be first managed with administration of tocilizumab.

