7.3.3 Modification of CTC Grading scale for Cytokine Release Syndrome (CRS)

The CTCAE grading system was developed to capture a cytokine release syndrome occurring during infusional therapy and is inadequate to capture the delayed CRS that occurs after CART-19 infusions. We propose to modify the CTC grading specifically to capture toxicity for protocols using CART-19 cells (Table 7.2.5a). Related definitions can be found in **Table 7.2.5b**.

Recipients of CART-19 cells may develop a cytokine release syndrome. Data from small numbers of patients show marked elevations in IL6, IFN-g, and less intensely TNF among other cytokines. Elevations in clinically available markers of inflammation including ferritin and CRP have also been observed to correlate with the clinical CRS syndrome.

Symptoms usually occur 1-14 days after cell infusion, but the syndrome is not defined by the timing of the reaction. Patients developing any symptoms attributable by the investigator as related to cytokine release should be reported as having had a CRS. Symptoms may include:

- High fevers
- Rigors
- Sweating
- Nausea
- Vomiting
- Anorexia
- Fatigue
- Headache
- Myalgia/arthralgia
- Hypotension
- Dyspnea
- Tachypnea
- Hypoxia
- Altered mental status
- End organ dysfunction
- Signs of macrophage activation syndrome including hemophagocytosis and hemolysis

For the purposes of reporting and grading on clinical trials using CART-19 cells, we will use the following grading for CRS Toxicity. The start date of CRS is a retrospective assessment of the date of onset of persistent fevers and/or myalgia consistent with CRS and not explained by other events (i.e. sepsis). The stop date of CRS is defined as the date when the patient has been afebrile for 24 hours and off vasopressors for 24 hours.

This document is confidential and the property of the University of Pennsylvania. No part of it may be transmitted, reproduced, published, or used by other persons without prior written authorization from the regulatory sponsor.

Table 7.2.5a - CRS Toxicity Grading				
1	2	3	4	5

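### Section 8.1.1 leaves open which grades of cytokine release syndrome count as toxicity failures, and neither reading matches the failure rate defined there as discontinuation

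*Combined protocol and SAP*

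**What the plan says.** Section 8.1.1 classifies patients in three ways within a few lines.

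- **Success** requires at least one dose and "the lack at least possibly related adverse events leading to permanent discontinuation of pembrolizumab".
- **Toxicity failure** has two limbs. The first is "Patients who experience Grade 3 or higher non-hematologic toxicity leading to permanent pembrolizumab discontinuation". The second is "any Grade 4 non-hematologic toxicity or cytokine release syndrome at least possibly related to pembrolizumab will be considered toxicity failures".
- **The monitored quantity** is defined by discontinuation: "We will denote the rate of pembrolizumab discontinuation as failure rate, FR". The trial stops if the posterior probability that FR exceeds 0.30 reaches 97.5%, with printed boundaries from 3/3 to 7/12.

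Two other sections bear on CRS.

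- Section 2.1 describes the primary safety endpoint as the discontinuation rate together with the rate of treatment-related events. Those events are related Grade 3 or higher events, with CRS named at Grade 4: "definitely related to study treatment or grade 4 cytokine release syndrome".
- Section 5.2.1.2 gives the CRS dose rule: "If patients develop cytokine release syndrome grades 1-3 after pembrolizumab, then pembrolizumab will be held until cytokine release syndrome resolves". Restarting is then optional. Drug is stopped for toxicity at Grade 4, or if tocilizumab is required.

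The trial summary, section 3.1, section 4.2.3.1 and the hypothesis in 8.1.1 all state the 30% criterion as toxicity resulting in discontinuation.

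**The concern.** The failure sentence supplies the numerator of the stopping rule and of the final safety rate, yet it can be read in two ways. Grade 4 may govern both nouns, or it may govern only non-hematologic toxicity and leave CRS ungraded. Neither reading fits the success and FR definitions beside it, because those depend on permanent discontinuation and the second failure limb does not.

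CRS is the toxicity on which this matters most. The trial anticipates that pembrolizumab may re-activate CAR T cells, and section 5.4.2 says that "some degree of CRS may be a desired clinical outcome". Section 7.3.3 also sets a low threshold for recording it: "Patients developing any symptoms attributable by the investigator as related to cytokine release should be reported as having had a CRS". In an open-label trial of 12 patients, a stopping decision or the primary safety conclusion could turn on how this sentence is read after the events are known.

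**Working it through.** **1. How each definition classifies a patient whose only event is related CRS.** The inputs are the definitions in 8.1.1 and the dose rule in 5.2.1.2.

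| CRS course | Success? | In FR (discontinued)? | Failure, any-grade reading | Failure, Grade 4 reading |
|---|---|---|---|---|
| Grade 1-2, held, drug resumed | yes | no | yes | no |
| Grade 1-2, tocilizumab required, drug stopped | no | yes | yes | no |
| Grade 3, held, drug resumed | yes | no | yes | no |
| Grade 3, drug permanently stopped | no | yes | yes | yes (first limb) |
| Grade 4, drug stopped | no | yes | yes | yes |

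The any-grade reading disagrees with FR in rows 1 and 3, where one patient is both a success and a failure. The Grade 4 reading disagrees in row 2, where the patient is neither. Section 2.1 does not settle row 3 or row 4, since it is unclear whether Grade 3 CRS falls under its Grade 3 or higher events.

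**2. Effect on the final rate, with no assumed rates.** At n = 12 the criterion of at most 30% allows 3 failures (3/12 = 25%; 4/12 = 33.3%).

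- Four patients with mild CRS who resume drug, no other event: 0/12 on the Grade 4 reading (met), 4/12 on the any-grade reading (missed).
- One other failure plus six such patients: 1/12 (8.3%) against 7/12, which is the printed stopping boundary.
- Such CRS in each of the first three patients reaches 3/3 on the any-grade reading only.

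**3. The plan's own boundaries.** The posterior is Beta(1 + r, 1 + n - r) for r failures in n patients. Seven of the ten printed boundaries are the smallest r with Pr[FR > 0.30] of at least 0.975. The other three fall short: 3/4 gives 0.9692, 4/6 gives 0.9712 and 5/8 gives 0.9747. That is a separate matter. The boundaries do not depend on the CRS definition, and the printed ones are used below.

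**4. Effect on the chance of stopping.** The documents give no CRS rate after pembrolizumab, so these rates are assumptions. Let f = 0.05 be the rate of other failures and q the rate of Grade 1-3 CRS, independent of them. The failure probability is f on the Grade 4 reading and 1 - (1 - f)(1 - q) on the any-grade reading; for q = 0.20 that is 1 - 0.95 × 0.80 = 0.240. An exact recursion over 12 patients, checking the printed boundaries after each, gives:

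| Reading | q | Failure probability | Chance of stopping | Chance of completing with at most 3/12 |
|---|---|---|---|---|
| Grade 4 | any | 0.050 | about 0.1% | 99.7% |
| Any grade | 5% | 0.0975 | 0.4% | 97.5% |
| Any grade | 10% | 0.145 | 1.4% | 91.4% |
| Any grade | 20% | 0.240 | 6.7% | 67.5% |
| Any grade | 30% | 0.335 | 18.8% | 38.4% |
| Any grade | 40% | 0.430 | 38.1% | 16.5% |

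With f = 0.10 the chance of stopping is 0.4% on the Grade 4 reading. On the any-grade reading it is 3.2%, 10.9%, 25.2% and 45.2% at q = 10%, 20%, 30% and 40%.

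**The case against.** A reader might infer that 8.1.1 plainly makes any CRS, even Grade 1, a failure. The argument is that Grade 4 CRS is already a Grade 4 non-hematologic toxicity, so naming CRS adds something only if lower grades count. The documents do not support going that far. Grade 4 can govern both nouns, just as the relatedness phrase that follows covers both. Section 2.1 also names Grade 4 CRS beside Grade 3 or higher events, so the authors list it separately elsewhere. They have a reason to, because CRS has its own grading scale in 7.3.3. The success and FR definitions point the same way: a patient with mild CRS who resumes drug has not discontinued.

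The figures also need care. At CRS rates of 5% to 10% the chance of stopping is only 0.4% to 1.4%. The model treats every Grade 1-3 case as a non-failure on the Grade 4 reading, which overstates the contrast, because Grade 3 CRS with permanent discontinuation already meets the first limb. Section 7.3.3 requires the investigator to attribute symptoms to cytokine release, and it dates onset from persistent fever or myalgia not otherwise explained. The any-grade category is therefore not unlimited.

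All of that stands. It makes the Grade 4 reading the more likely intention, but the failure sentence does not say so, and that reading still leaves the tocilizumab case unclassified. Section 2.1 cannot simply be copied across either, because it also counts related Grade 3 or higher events whether or not drug is discontinued.

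**Conclusion.** The point holds as an ambiguity and an internal inconsistency. It does not show that the plan definitely counts mild CRS as failure. The scope of Grade 4 over CRS is open, and each reading departs from FR in a different direction: one adds patients who did not discontinue, the other omits patients who did.

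The 0/12 against 4/12 contrast rests on the wording alone, given four such patients. The stopping probabilities, 0.4% to 38.1% against about 0.1%, rest on an assumed 5% base failure rate, assumed Grade 1-3 CRS rates of 5% to 40%, independence, and the printed boundaries. The effect is small if CRS is rare and decisive if it is common. Because the sentence feeds both the stopping rule and the primary safety conclusion, it should be settled before those counts are made.

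**What to change.** The sponsor should reconcile sections 2.1, 5.2.1.2 and 8.1.1 into one explicit CRS criterion that:

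- states the CRS grade or grades that count as failure, by Table 7.2.5a;
- states how CRS below that grade is counted when it leads to permanent discontinuation, including after tocilizumab;
- makes success and failure complementary, so that every evaluable patient falls in exactly one;
- is used unchanged for FR in the stopping rule and for the final safety rate.

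All CRS should also be reported separately by grade, whether or not it counts. Adding Grade 4 to the CRS limb alone would not be enough, because the tocilizumab case would remain unclassified. Which grade counts is for the sponsor to state.

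The cost is a few words in 8.1.1 and a matching edit in 2.1. No new data are needed: CRS grade, action taken with drug and concomitant medication are already recorded.
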